5.10 Assessments for Untreated Delayed-Treatment Control Subjects

If a delayed-treatment control subject is not eligible to be dosed, and the subject agrees to remain on study, the subject will be followed up to Month 30 (from enrollment) as per the Schedule of Events in [Section 5.7](#).

5.11 Amount of Blood (UNIQUE to France)

Blood Samples for:	Blood Volume per Visit
Genetic testing (central lab)	3 mL
Safety labs (hematology) (central lab)	0.5 mL
Safety labs (hematology) (local lab)	0.5 mL
Safety labs (chemistry) (central lab), including cytokine panel and Troponin T and/or I	2.5 mL
Safety labs (chemistry) (local lab)	2.0 mL
Complement panel (central lab)	3.2 mL
Coagulation parameters (central lab)	1.8 mL
Anti-AAV8 NAb and TAb, and anti-MTM1 antibody (central lab)	2.5 mL
IFN- γ (PBMCs) (central lab)	4.0 mL
HLA typing (central lab)	2.0 mL
Serum bile acid assay (fasting preferred; central lab)	1.0 mL

Anti-AAV8 = anti-adenovirus 8; anti-MTM1 = gene that codes for myotubularin (a mutation in the *MTM1* gene results in myotubular myopathy); HLA = human leukocyte antigen; IFN- γ = interferon-gamma; NAb = neutralizing antibody; PBMCs = peripheral blood mononuclear cells; TAb = total antibody.

6 ADVERSE EVENT MANAGEMENT

6.1 Adverse Events

6.1.1 Definition of Adverse Events

According to the ICH 2EA guideline Definitions and Standards for Expedited Reporting and 21 CFR 312.32, IND Safety Reporting, an AE is any untoward medical occurrence associated with the use of the IMP in a study subject whether or not considered drug-related. An AE can therefore be any unfavorable and/or unintended sign, symptom, or disease temporally associated with the use of an IMP or study procedure, whether or not considered related to the IMP. This definition includes the following:

- Any pre-existing condition that increases in severity or changes in nature during or as a consequence of the IMP treatment administration or study procedure.
- All AEs (regardless of relationship to IMP) should be recorded from the Baseline Visit (Day -2 to -1) through the end of the safety reporting period.
- AEs occurring as a result of product withdrawal, abuse, overdose
- A change in a laboratory test results (eg, hematology, clinical chemistry, or urinalysis) or other safety assessments (eg, ECG, radiological scans, vital signs measurements) if considered by the Investigator to be clinically significant or if it caused (or should have caused) the Investigator to initiate a non-protocol therapy or procedure (refer to [Section 6.5](#) for further details regarding assessment of abnormal laboratories). This includes results that worsen from baseline.

An AE does not include the following:

- Elective surgery or procedures for pre-existing conditions that are stable and have not worsened (eg, hospitalization for elective surgery, social and/or convenience admissions).
- Pre-existing diseases, conditions, or laboratory abnormalities present or detected before the IMP administration that do not worsen; such events should be recorded in the medical history eCRF.
- Any medical condition or clinically significant laboratory abnormality with an onset date before the consent form is signed and not related to a protocol-associated procedure is not an AE. It is considered to be pre-existing and should be documented on the medical history eCRF.

The Investigator and any qualified designees are responsible for detecting, documenting and recording events that meet the definition of an AE or SAE and remain responsible for following up AEs that are serious, considered related to AT132 and other study treatments or procedures, or that caused the subject to discontinue the study.

6.1.2 Adverse Event Reporting and Collection Period

The Investigator is responsible for monitoring the safety of subjects who have entered this study and for providing appropriate medical care.

The Investigator is responsible for evaluating all AEs, obtaining supporting documents, and for final review and confirmation of accuracy and completeness of event information and documentation. All SAEs will be reported on the eCRF and SAE worksheet. All AEs will be reported on the eCRF.

If the National Cancer Institute Common Terminology Criteria for AEs (NCI-CTCAE) grade of an SAE/AE changes, the event should be relisted on the eCRF, and SAE worksheet for SAEs, with the new NCI-CTCAE grade and new onset date.

The exception is ongoing pre-dose events that continue post-dose and improve post-dose. Such events should not be re-listed.

If the NCI-CTCAE grade of an SAE reduces, the details of the AE should be provided on the SAE worksheet for the medical assessor to be able to assess the course of the event.

6.1.3 Start of Adverse Event Collection Period

If a subject experiences an AE after the informed consent document is signed, but before the Baseline/Control Baseline visit, the event will be considered medical history.

If a control subject experiences an AE after the Control Baseline visit but before the Baseline visit prior to dosing, the event will be considered a Control AE.

If the subject experiences an SAE after signing consent and before Baseline, it should only be reported as an SAE if the Investigator believes that the event may have been caused by a protocol-required procedure.

6.1.3.1 Ongoing Adverse Event Collection During the Study

Before the Baseline visit, site personnel will note the occurrence and severity of each medical condition for the subject. During the study, site personnel will note any change in the severity of Baseline medical condition(s) and the occurrence and nature of any AEs. Whenever possible, an integrated diagnosis should be given for AE signs and symptoms of a common pathology. When recording AEs/SAEs, describe the event using commonly accepted medical terminology, if possible.

The details of each event should be discussed with the subject. If the event is serious, it must be reported to the Sponsor or its designee **within 24 hours** of the Investigator/designee/site personnel learning of the event.

6.1.3.2 End of Adverse Event Collection Period

AEs will be collected and reported until the subject completes the study or withdraws from the study.

AEs and SAEs will be followed as clinically indicated until resolution or, if non-resolving, until considered stable or until the end of the AE collection period, whichever comes first.

The Sponsor retains the right to request additional information for any study subject with ongoing AE(s)/SAE(s) at the end of the study, if judged necessary.

Investigators are not obligated to actively seek AEs or SAEs after conclusion of the study participation. However, if the Investigator learns of any SAE, including a death, at any time after a subject has been discharged from the study, and the event is considered to be reasonably related to the study drug or study participation, the Investigator must promptly notify the Sponsor.

6.1.3.3 Recording and Assessment of Seriousness, Severity, and Causality

It is the responsibility of the Investigator to review all documentation (eg, hospital progress notes, laboratory reports, and diagnostics reports) related to the event. Assessment of AEs must include seriousness, severity, relationship to study drug, duration, and outcome. At the Screening Visit, site personnel will note the occurrence and severity of each medical condition for the subject and document in Medical History. During the study, site personnel will note any change in the severity of medical condition(s) and the occurrence and nature of any AEs. Use precise medical terminology when recording AEs or SAEs. Record only 1 diagnosis, sign, or symptom in the AE eCRF (eg, nausea and vomiting should not be recorded in the same entry, but as 2 separate entries).

Whenever possible, a diagnosis should be recorded as the AE term rather than a series of terms relating to a diagnosis. If the diagnosis is unknown, record sign(s) and/or symptom(s). If a diagnosis subsequently becomes available, the diagnosis should be recorded, replacing the original entry(s) where appropriate.

The details of each event should be discussed with the subject.

All SAEs will be recorded and reported to the Sponsor or designee immediately and under no circumstance should this exceed 24 hours. The Investigator will submit any updated SAE data to the Sponsor **within 24 hours** of it being available.

The Sponsor retains the right to request additional information for any study subject with ongoing AE(s)/SAE(s) at the end of the study, if judged necessary. The Investigator will evaluate all AEs considered ongoing at the end of the study and document whether event has resolved, resolved with sequelae, or stabilized, with update to source and eCRF as appropriate.

It is not acceptable for the Investigator to send photocopies of the subject's medical records to the Sponsor in lieu of completion of the SAE worksheet. There may be instances when copies of medical records for certain cases are requested by the Sponsor. In this case, all subject identifiers, with the exception of the subject number, will be redacted on the copies of the medical records before submission to the Sponsor.

6.1.3.4 Eliciting Adverse Events

The site personnel will instruct the subject to report any changes in health or new symptoms they notice during the study. At each visit, AEs should be elicited with minimal connotations. Care will be taken not to introduce bias when detecting AEs and/or SAEs. For example: “Have you had any health problems since your last visit?”

6.2 Serious Adverse Events

6.2.1 Definition of Serious Adverse Events

An SAE is defined as any untoward medical occurrence at any dose that results in the following:

- Death
- Life-threatening (The term “life-threatening” in the definition of “serious” refers to an event that, in the view of either the Investigator or Sponsor, places the subject at risk of death at the time of the event; it does not refer to an AE that hypothetically might have caused death if it were more severe.)
- Requires inpatient hospitalization or prolongs existing hospitalization
- Elective surgery or procedures for preexisting conditions that are stable and have not worsened (eg, hospitalization for elective surgery, social and/or convenience admissions) are not considered SAEs; however, an event that prolongs this type of hospitalization would be considered an SAE
- Persistent or significant disability/incapacity (The term disability means a substantial disruption of a person’s ability to conduct normal life functions).
- A congenital anomaly/birth defect
- An important medical event that may not result in death, be life-threatening, or require hospitalization, but may be considered an SAE when, based upon appropriate medical judgment, it may jeopardize the subject or may require medical or surgical intervention to prevent one of the other outcomes listed in the above definition. These important medical events should usually be considered medically significant, and therefore serious. Examples of such events include invasive or malignant cancers, intensive treatment in an emergency room or at home for allergic bronchospasm, blood dyscrasias, or convulsions that do not result in hospitalization. Potential drug induced liver injury (DILI) should be considered a medically significant event.

6.2.2 Serious Adverse Event Reporting Requirements

Prompt notification by the Investigator to the Sponsor of a SAE is essential so that legal obligations and ethical responsibilities towards the safety of subjects and the safety of a study drug under clinical investigation are met. The Investigator must complete and submit an SAE worksheet containing all information that is required by local and/or regional regulations to the Sponsor by fax or email immediately (**within 24 hours** of awareness).

The SAE worksheet must be signed by a medically qualified Investigator (as identified on delegation of authority log). Signature confirms accuracy and completeness of the SAE data, as

well as the Investigator causality assessment including the explanation for the causality assessment.

Regardless of whether the SAE is deemed related to use of the IMP or study procedure, the data for the SAE must be reported with the appropriate information to the Sponsor or its designee **within 24 hours** of Investigator/designee/site personnel learning of the event. The Sponsor's Medical Monitor or designee may be contacted at any time for immediate discussion regarding such an event.

Please refer to the Study Management Plan for additional guidance regarding SAE reporting to the Sponsor.

Sites must report all SAEs to their governing IRB/EC, as required by local regulations and guidelines.

The Investigator is encouraged to discuss with the Medical Monitor any AEs for which the issue of seriousness is unclear or questioned. Contact information for the Medical Monitor can be found in the study contact list.

All deaths, regardless of causality, occurring from the time the subject signs the ICF until the Month 60 Visit are to be reported as SAEs to the Sponsor or its designee **within 24 hours** of the Investigator, designee, and/or site personnel's awareness of the event. For fatal or life-threatening events, copies of hospital case reports, autopsy reports, and other documents are also to be submitted by email or fax when requested and applicable. Any supportive SAE documentation (eg, hospital records, autopsy reports, progress notes) provided to the Sponsor or its designee should have all personal subject identification fully redacted in accordance with governing privacy regulations.

Additional information may be requested by the Sponsor or its designee to ensure the timely completion of accurate safety reports.

Any medications necessary for treatment of the SAE must be recorded onto the medication section of the subject's eCRF and the event description of the SAE.

6.2.2.1 Follow-Up of Serious Adverse Events

After the initial SAE report, the Investigator is required to proactively follow each subject at subsequent visits/contacts. All SAEs will be followed until resolution, stabilization, the event is otherwise explained, or the subject is lost to follow-up. New follow-up data for SAEs must be reported **within 24 hours** of receipt. All SAEs will be followed as clinically indicated until resolution or, if non-resolving, until considered stable or until the end of the AE collection period ([Section 6.1.2](#)) whichever comes first.

6.2.2.2 Serious Adverse Event Onset and Resolution Dates

The onset date of the SAE is defined as the date the event meets the criteria of a serious event. The resolution date is the date the event no longer meets the criteria of a serious event, the

date the symptoms resolve, or the event is deemed chronic. In cases of hospitalizations, the hospital admission date is considered the onset date.

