- ^z The PedsQL is to be performed for all subjects, regardless of age. Subjects < 2 years of age should be administered the version for 2- to 4-year-olds.
- ^{aa} See [Appendix 5](#). At baseline, the CGI-S is conducted for all subjects. At baseline, the CGI-I is conducted only for control subjects who are attending their second baseline before treatment with AT132.

- ^{bb} Parents/LARs/caregivers (the same person every time, whenever possible) in ASPIRO will be asked to complete forms for subjects 8 months and older.
- ^{cc} Subjects will be administered a course of glucocorticoid therapy commencing Day -1 and continuing for a period of 16 weeks as a preventative measure for immune-mediated hepatic injury. For subjects weighing < 60 kg, the dose will be 1 mg/kg prednisolone orally daily for 8 weeks, then tapered down for 8 weeks per Investigator discretion. For subjects weighing ≥ 60 kg, the dose will be 60 mg prednisolone orally daily for 8 weeks, then tapered down for 8 weeks per Investigator discretion.
- ^{dd} Ursodiol to be dosed at 20 mg/kg/day (divided either BID or TID at the Investigator's discretion), beginning approximately 1 week (ie, between Days -6 and -4, at the Investigator's discretion) before AT132 administration and continuing to Week 12.
- ^{ee} As of protocol v9: Subjects yet to be dosed will be administered 1.3×10^{14} vg/kg AT132 (see [Section 1.4.2](#)).
- ^{ff} Subject may be admitted to the study clinic on Day -2 or -1 for baseline procedures, including confirmation of baseline ventilator settings. If medically appropriate, subject may be discharged from the study clinic after completion of Day 2 assessments.
- ^{gg} Viral shedding will be assessed on samples of saliva (swab), stool, and urine (diaper collection or urine bag). Collection of each sample type will begin on Day 1 and will continue until each sample type has 3 consecutive data points at or below the limit of detection (BLOD) (see [Section 5.1.1.27](#)). Sponsor will notify site when collection can cease. Not conducted at Week 6.

5.5 Schedule of Events for Subjects Treated with AT132: Week 9 – Month 60

Study Phase/Visit	Daily	Weeks 9, 10, 11	Week 12	Weeks 13, 14, 15	Week 16	Weeks 20, 28, 32, 40, 44	Week 24	Week 36	Week 48 or Early Withdrawal	Month 15	Months 18, 24, 30, 36, 42	Months 48, 54, 60
Study Day(s)	NA	63, 70, 77	84	91, 98, 105	112	140, 196, 224, 280, 308	168	252	336	456	548, 730, 913, 1095, 1278	1460, 1643, 1825

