7.4.1.1 Adverse Events

AEs will be coded using the Medical Dictionary for Regulatory Activities (MedDRA) dictionary.

Events will be identified as treatment-emergent (TEAE) and non-treatment-emergent (non-TEAE) on the basis of the date of onset relative to the date of AT132 dosing.

Number and percentage of subjects with TEAEs classified by system organ class (SOC) and preferred term (PT); by severity, causality, seriousness, and action taken with regard to study drug will be summarized. Number (%) of subjects with TEAEs leading to discontinuation of study will also be summarized. Hospitalization will be summarized by frequency (%) and duration. TEAEs and/or hospitalizations may be annualized.

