4.6.1 Adverse Events

Treatment-emergent AEs (TEAEs) are defined as any AEs, regardless of relationship to study drug, that have an onset or worsening in severity on or after the time/date of the baseline (dosing) visit (the reference date).

All descriptive statistics will be presented by dose level and all dose levels combined. Unless otherwise indicated, AE summaries will be presented by the following periods:

- Baseline through Week 24 (inclusive)
- >Week 24 through Week 48
- >Week 48 to End of Study
- Overall for the study

An overview table to report the number and percentage of participants and number of events will include the following:

- TEAEs,
- Drug related TEAEs,
- Serious TEAEs,
- Serious drug related TEAEs,
- TEAEs leading to withdrawal of study
- Drug-related TEAEs leading to withdrawal of study
- TEAEs leading to death,
- Drug related TEAEs leading to death,
- NCI-CTCAE Grade 3 or higher TEAEs
- NCI-CTCAE Grade 3 or higher drug related TEAEs
- Deaths

NCI-CTCAE v4.03 or higher will be used for assessment of grade.

The number and percentage of participants with TEAEs, as classified by SOC and PT will be summarized for each treatment group and overall. Summaries will be provided for the following:

- TEAEs
- Drug related TEAEs,
- Serious TEAEs,
- Drug related serious TEAEs,
- TEAEs leading to withdrawal of study,
- Drug related TEAEs leading to withdrawal of study,
- NCI-CTCAE Grade 3 or higher TEAEs,
- NCI-CTCAE Grade 3 or higher drug-related TEAEs,
- TEAEs leading to death,
- Drug-related TEAEs leading to death,
- Frequently reported ($\geq 10\%$ in All Dosed Group) TEAEs by preferred term,
- Frequently reported ($\geq 5\%$ in Any Treatment Group) TEAEs Excluding Serious TEAEs (this table will only be presented for the overall study duration)

Related AEs are those with relationship to study medication reported as “possible” or “related”. If relationship to study drug of an AE reported by treated participants is not recorded, the relationship will be imputed as “possibly related”, for analysis purposes. In the participant listing, both collected and imputed values will be presented.

An overview table to report number of events, and events adjusted by participant year from date of drug exposure (each summary classified by category below, SOC and PT) will include the following:

- Serious respiratory TEAEs,
- Serious non-respiratory TEAEs

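### Protocol 6.2.2.2 gives two conflicting onset dates for an SAE that arises during an existing hospital stay, and one of them can make a post-dose event non-treatment-emergent

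*Protocol*

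**What the plan says.** Protocol 6.2.2.2 opens with a general rule: "The onset date of the SAE is defined as the date the event meets the criteria of a serious event". It ends with a specific one: "In cases of hospitalizations, the hospital admission date is considered the onset date". The specific rule has no exception for a child who is already in hospital when the event occurs.

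Protocol 6.2.1 makes such events reportable. One seriousness criterion reads "Requires inpatient hospitalization or prolongs existing hospitalization". For elective, social or convenience admissions, which are not themselves SAEs, the protocol adds that "an event that prolongs this type of hospitalization would be considered an SAE".

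The onset date then decides how the event is analysed. Protocol 7.4.1.1 separates treatment-emergent from other events "on the basis of the date of onset relative to the date of AT132 dosing". SAP 4.6.1 counts as treatment-emergent those AEs "that have an onset or worsening in severity on or after the time/date of the baseline (dosing) visit".

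Admission before dosing is part of the design. A footnote to the treated-subject schedule (Protocol 5.4) says: "Subject may be admitted to the study clinic on Day -2 or -1 for baseline procedures". Dosing is on Day 1.

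**The concern.** A hospitalisation is a reasonable marker of when an event became serious if the event caused it. If the child was already in hospital, the admission date can precede both the event and the dose. The closing sentence of 6.2.2.2 does not separate these cases, so two sites following the same paragraph could record different onsets for the same event. One of those onsets takes the event out of the TEAE tables.

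The stakes are higher than usual because SAP Section 2 drops hypothesis testing. The descriptive safety tables by dose are now a main product of the trial, and the groups are small. Serious, drug-related and special-interest events are all tabulated as TEAEs in SAP 4.6.1, so an event dated before dosing is missing from all of them.

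**Working it through.** The plan states no figure to reproduce. The check applies the date rules to constructed cases, then looks for anything that would correct the result, then sizes the effect.

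**Step 1. Apply each sentence of 6.2.2.2 to an event arising in a stay begun before dosing (dosing = Day 1).**

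| Case | Onset by first sentence (became serious) | TEAE status | Onset by last sentence (admission) | TEAE status |
|---|---|---|---|---|
| Admitted Day -2; new event on Day 2 prolongs the stay | Day 2 or later | TEAE | Day -2 | Not a TEAE |
| In hospital since Day -20; new event on Day 28 prolongs the stay | Day 28 or later | TEAE | Day -20 | Not a TEAE |

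The first row applies only if the Day -2 or -1 study-clinic admission counts as a hospitalisation. The second row does not depend on that. Protocol 1.1 reports that some children with this disease stay in hospital throughout their first years, and the criteria in 3.3.1 and 3.3.2 do not exclude inpatients.

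**Step 2. Look for a rule that restores the event.**

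- The worsening limb of the SAP definition, and the relisting of an event under a new onset date when its grade changes (Protocol 6.1.2), recover only events whose grade worsens after dosing. A new event of constant grade is not recovered.
- SAP 4.10.3 imputes onset dates only when they are missing or incomplete. An admission date is complete, so it stays.
- SAP 4.6.1 has no step that compares a recorded SAE onset with the date the event arose.

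**Step 3. Size.** Inputs are from Protocol 1.4.2, data cutoff 08 July 2020: 17 children at the high dose, of whom 8 had AT132-related SAEs; 6 at the low dose, of whom 1 had them.

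- One child, high dose: 1/17 = 5.9 percentage points. For example, 8/17 = 47.1% would become 7/17 = 41.2%.
- One child, low dose: 1/6 = 16.7 points. For example, 1/6 = 16.7% would become 0/6 = 0%.

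These are changes in the percentage of children, so they assume that the child has no other event in the same table. That will often be false: the 8 high-dose children had 26 related SAEs (26/8 = 3.25 each) and the one low-dose child had 4. The SAP also tabulates numbers of events, and those counts fall by one for each misdated event whatever else the child had.

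**The case against.** The strongest reply is that the first sentence of 6.2.2.2 governs and the last only illustrates it. An event that requires admission becomes serious at admission; an event that prolongs a stay becomes serious when it does so, which is after dosing. The other reading would date a reaction before the drug was given, at odds with the temporal test for relatedness in Protocol 6.3.2. This is probably what was meant, and it is why the point is a conflict between two sentences and not a rule that plainly discards events. But the last sentence is the more specific one and is unqualified, and nothing in the SAP checks which date a site entered.

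The factual footing is also thin. The documents call the pre-dose stay an admission to the study clinic, and Protocol 1.1 describes the disease population, not the trial children at dosing. No document says that any child was a hospital inpatient when dosed. That limits the likely number of affected records; it does not settle the rule.

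The SAP reference point, which names baseline and dosing together, could be read as the Day -2 to -1 visit. On that reading an admission on the visit day might still count as treatment-emergent. Protocol 7.4.1.1 says dosing, however, and the reading does not help a stay that began earlier.

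A reader might go further and infer that the rule is also wrong because it moves events later, past the Week 24 or Week 48 cut-off, when signs begin at home and admission follows. The documents do not support calling that an error. The shift follows from dating an SAE from when it became serious, which is a defensible convention, and it leaves the overall-study tables unchanged. Nor would early liver signals be lost: Protocol 6.3.1, 6.4 and 6.5.3 require laboratory abnormalities to be reported in their own right, 6.1.2 relists grade changes, and SAP 4.6.2.2 summarises liver tests by period.

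A reader might likewise object that 6.2.2.2 lets an event resolve once it is judged chronic. No TEAE or period assignment uses the resolution date, so this is a side issue.

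**Conclusion.** The conflict is real and narrow. For an SAE that arises during a stay already under way at dosing, 6.2.2.2 supports both a post-dose and a pre-dose onset, and the pre-dose one removes a constant-grade event from the serious, drug-related and special-interest TEAE tables.

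If it happened to one child with no other serious TEAE, incidence would change by 5.9 points at the high dose or 16.7 points at the low dose, on the July 2020 denominators. This rests on the last sentence being applied literally, on the event not worsening in grade after dosing, and, for a dosing-visit stay, on that stay being treated as a hospitalisation. The documents do not show that any record was affected. A reader might infer that acute post-infusion SAEs have in fact been dropped; nothing in the documents supports that.

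**What to change.** **Protocol 6.2.2.2:** limit the admission-date rule to events that caused the admission. State that an event which arises, or becomes serious, during an existing stay is dated from the day that happened.

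**SAP 4.6.1:** base treatment-emergence on the date the event first arose or worsened, relative to dosing, and name dosing alone as the reference point.

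**Data:** before database lock, query every SAE whose recorded onset is before dosing and equals an admission date, and correct the onset from source where needed.

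**Cost:** two sentences and a small retrospective query. Because dosing has ended, the wording change alone will not correct dosing-stay records; the query does that work. Nothing is lost by freeing the onset field, since SAP 4.6.2.5.3 already uses separate admission and discharge dates for length of stay. No child has an extra visit or procedure.
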